2.3.2. Treatment Groups and Reporting Periods for Analysis

In the study schematic in Figure 1, the study period and treatment groups to be included in the primary analysis are encircled in red.

- Treatment groups:
 1. fordadistrogene movaparvovec – participants randomized to Cohort 1 to receive a single dose of fordadistrogene movaparvovec on Day 1 (Year 1 Day 1).
 2. Placebo – participants randomized to Cohort 2 to receive a single dose of placebo on Day 1 (Year 1 Day 1).

- Reporting Period:

All analyses will be relative to Day 1 (Year 1 Day 1) investigational product (IP) administration.

The reporting period will include all data from the day of the Year 1 Day 1 IP administration through Week 52. Specifically, all participant data from Day 1 to the earliest of (1) Day 390 (the upper limit of the Week 52 analysis visit window or (2) one day before the Year 2 Day 1 IP administration.

2.3.3. Siblings

When ≥ 2 brothers meet all the study entry criteria, they will all be enrolled in the study simultaneously. One of the brothers will be defined as the “participant” and the other(s) will be defined as the “sibling(s)”. The sibling(s) will not be randomized but they will receive the same treatment with approximately the same timing (as long as the siblings were strictly separated from each other until both have received IP) and sequence based on the Cohort to which the participant is randomized. The sibling(s) will participate fully in the double blind study as a participant, complete all visits and evaluations, and comply with all protocol requirements. Data from the sibling(s) will not contribute to the main analyses of the primary and secondary endpoints. A supplementary analysis of the primary endpoint, NSAA, will include data from the sibling(s). Data from the sibling(s) will be included in all analyses of safety.

For analysis purposes, the “participant” and the “sibling” will be identified by specific ranges of randomization numbers. Two separate randomization lists will be created; one for participants age < 6 years and one for participants age ≥ 6 years. Each eligible participant will be randomized and receive a randomization number from the appropriate randomization list starting with the lowest randomization number. Sibling(s) will be manually assigned a randomization number in the IRT system by the IRT support team. The IRT support team will start at the end of the appropriate randomization list and working backward select the first un-assigned randomization number that will provide the same treatment as that randomly assigned to the participant.

- “Participants” will be those with a randomization number from 1-300 or 1001-1300, depending on their stratum assignment.
- “Siblings” will be those with randomization numbers from 301 to 996 or 1301-1996, depending on their stratum assignment.

If the participant is randomized within the first approximately 15 participants (with the potential to collect a maximum of 33 if needed) collecting muscle biopsies, muscle biopsies will be collected from him and his sibling(s). Biopsy data from the sibling(s) will be excluded from the main analyses of mini-dystrophin in this study, but will be included in supplementary analyses of the secondary endpoints.

3. ENDPOINTS AND BASELINE VARIABLES: DEFINITIONS AND CONVENTIONS

3.1. Primary Endpoint(s)

Change from Baseline at Week 52 in the NSAA total score.

The NSAA is a 17-item test that grades performance of various functional skills using the following scale: 0 (unable to achieve independently), 1 (modified method but achieves goal independent of physical assistance from another), and 2 (“normal”- no obvious modification of activity) [Mazzone et al., 2009]². The NSAA total score is calculated as the sum of the individual item responses and ranges from 0 to 34 with higher scores indicating better function.

If one or more of the 17 individual items is missing, the total score is set to missing.

3.2. Secondary Endpoint(s)

1. Change from Baseline in percent normal mini-dystrophin transgene protein expression level in biceps brachii muscle biopsies at Day 360 (Week 52) using an LC-MS assay

The LC-MS assay measures the LLQVAVEDR (LLQV) peptide that detects full-length endogenous dystrophin as well as the mini-dystrophin transgene protein. The expression level will be provided from the vendor and is expressed as %normal, with normal defined by full length dystrophin from non-dystrophic control samples. Levels below the LLOQ will be imputed as 0.5*LLOQ. The LC-MS assay also measures the LEMPSSLMLEVPTHR (LEMP) peptide which quantifies only the mini-dystrophin transgene levels. The baseline LEMP peptide level in the biceps brachii muscle biopsy is expected to be below the LLOQ due to the absence of the mini-dystrophin transgene prior to treatment.

2. Change from Baseline in percent of muscle fibers expressing mini-dystrophin transgene protein in biceps brachii muscle biopsies at Day 360 (Week 52) as assessed by immunofluorescence.

Muscle fibers expressing mini-dystrophin transgene protein will be evaluated by immunofluorescent staining using the mini-dystrophin specific antibody that only recognizes the mini-dystrophin transgene protein.

For the participant in Study C3391003 , a global threshold for calculating the percentage of mini-dystrophin positive fibers was applied based on all baseline samples from the 19 ambulatory participants

3. Change from baseline at Week 52 in serum CK concentration.

The CK results reported by the central laboratory and each local laboratory will be converted to conventional units of measurement, if necessary. These unit-standardized results will be used for analysis purposes.

4. Number of skills gained at Week 52 based on the individual items of the NSAA.

The number of skills gained at Week 52 is the total number of skills with a response of 0 at Baseline and a response of either 1 or 2 at Week 52.

5. Number of skills either improved or maintained at Week 52 based on the individual items of the NSAA.

The number of skills either improved or maintained at Week 52 is the total number of skills with:

- A response of 0 at Baseline and a response of either 1 or 2 at Week 52, or
- A response of 1 at Baseline and a response of 1 or 2 at Week 52, or
- A response of 2 at Baseline and a response of 2 at Week 52.

6. Change from Baseline at Week 52 in the 10 meter run/walk velocity.

Velocity in meter/second is defined as 10 times the reciprocal of the time to complete the 10 meter run/walk test. For participants with a score of 0 on the 10 meter run/walk item (NSAA item 17), velocity will be set to 0. For participants with a missing score on the 10 meter run/walk item (NSAA item 17), velocity will be set to missing.

7. Change from Baseline at Week 52 in the rise from floor velocity.

Velocity is defined as the reciprocal of the time to rise from floor. For participants with a score of 0 on the rise from floor item (NSAA item 12), velocity will be set to 0. For participants with a missing score on the rise from floor item (NSAA item 12), velocity will be set to missing.

8. Change from Baseline at Week 52 in the Modified PODCI: Transfer and Basic Mobility Core Scale (Pediatric Parent)

The Modified PODCI: Transfer and Basic Mobility Core Scale (Pediatric Parent) consists of 11 items and assesses a participant's ability to walk, stand, and perform activities of daily living. The scale produces an independent, standardized score ranging from 0-100, with lower scores representing lower levels of function.

The Modified PODCI: Transfer and Basic Mobility Core Scale (Pediatric Parent) standardized score is calculated as described in [Appendix 2.2.1](#)

9. Change from baseline at Week 52 in the Modified PODCI: Sports and Physical Functioning Core Scale (Pediatric Parent).

The Modified PODCI: Sports and Physical Functioning Core Scale (Pediatric Parent) consists of 21 items and assesses a participant's ability to walk, stand, and perform

activities of daily living. The scale produces an independent, standardized score ranging from 0-100, with lower scores representing lower levels of function.

The Modified PODCI: Sports and Physical Functioning Core Scale (Pediatric Parent) standardized score is calculated as described in [Appendix 2.2.1](#).

3.3. Other Endpoint(s)

Protocol specified tertiary/exploratory endpoints through Week 52 are defined below.

3.3.1. Efficacy Endpoints

1. Change from Baseline at Week 52 in passive ankle range of motion (dorsiflexion).

The degrees of passive dorsiflexion will be recorded for the left and right ankle.

2. Change from Baseline at Week 52 in real-life function parameters as assessed by actigraphy.

The following select set of daily measures from the 14 day observation period for each timepoint (Baseline, Weeks 9, 18, 35, and 52) will be analyzed:

- Steps per day (steps);
- 95th percentile of cadence (steps/min);
- Median cadence (steps/min);
- Percent time in high activity (%).

For each participant and for each parameter, the mean value across the daily measures will be calculated at each visit. If any day was considered non-compliant, the values from that day will not be included in the calculation of the mean. If a participant has at least 4 compliant days within the monitoring period, then the average across the compliant days will be included in the statistical analysis, otherwise, they will be treated as missing for that monitoring period (visit). These mean values will be used for the analysis of efficacy.

Compliance for each day is defined as:

- At least 22 hours of data collected on that day, which corresponds to at least 90% of data capture in a day;
- At least 300 steps recorded on that day;
- At least 100 active minutes recorded on that day;
- At least 30 steps within 5 consecutive hours (9am-7pm) recorded on that day.

3. Loss of ambulation through Week 52.

Loss of ambulation will be defined as:

- A caregiver report that the participant is not currently able to walk to perform activities of daily living (as determined by the Lowes Lab Ambulatory Status Algorithm), AND
- Inability to perform the walk item on the NSAA (unless considered temporary due to acute illness or injury) on the visit following the date on which the caregiver stated the participant lost the ability to ambulate.

The date for loss of ambulation will be recorded as the date reported by the caregiver as the last date on which the participant was able to walk to perform activities of daily living. This information will be collected on the same days that the NSAA is evaluated.

4. Change from Baseline at Week 52 in %pFVC

Note: Only collected in participants ≥ 6 years old at Screening. Spirometry will be performed using standardized equipment in accordance with the American Thoracic Society/European Respiratory Study Task Force: standardization of lung function testing guidelines 2005 [Miller et al., 2012]. Sufficient forced expiratory maneuvers (up to a maximum of 6) will be performed to produce at least 3 technically adequate tracings. The best (largest) FVC measurement from the set of 3 will be used to determine the FVC and the %pFVC according to age, height, race and gender [Quanjer et al., 2012] that are recorded on the CRF.

5. Response to each of the 5 dimensions of the EQ-5D-Y Proxy assessment at Week 52

The EQ-5D-Y Proxy is a recently developed generic instrument that measures the health status of children. The measure is completed by a caregiver and captures how he or she rates the health of the child. It was adapted from the original EQ-5D questionnaire developed by the EuroQol Group. The EQ-5D-Y Proxy includes five dimensions: mobility (walking around), selfcare (taking care of him/herself), usual activities (doing usual activities), pain/discomfort (having pain or discomfort), and anxiety/depression (feeling worried, sad or unhappy). Responses record three levels of severity: no problems, some problems, a lot of problems.

There is currently no index score for EQ-5D-Y, but if one becomes available, this will be included as an endpoint.

6. Change from Baseline at Week 52 on the EQ visual analog scale (VAS) proxy assessment.

The EQ-5D-Y Proxy also includes a standard vertical 20 cm visual analogue scale (EQ VAS) for recording current health-related quality of life on a scale from 0 to 100, with 0 representing the worst and 100 the best health state he or she can imagine.

3.3.2. QoL of Caregivers of Participants

1. Response to each of the 5 dimensions of the EQ-5D-5L assessment at Week 52 (caregivers of participants).

The EQ-5D-5L will be completed by caregivers regarding their own quality of life. The EQ-5D-5L descriptive system is comprised of 5 dimensions: mobility, self-care, usual activities, pain/discomfort, and anxiety/depression. Each dimension has 5 response levels: no problems, slight problems, moderate problems, severe problems, unable to/extreme problems.

2. Change from baseline at Week 52 in the EQ-5D-5L VAS assessment (caregivers of participants).

The EQ-5D-5L also includes a standard vertical 20 cm VAS for recording current health related quality of life on a scale from 0 to 100, with 0 representing the worst and 100 the best health state imaginable.

3. Change from baseline at Week 52 in the EQ-5D-5L index score (caregivers of participants).

The EQ-5D-5L index score is a single number summary of the responses to the 5 dimensions and reflects how good or bad a health state is according to the preferences of the general population of a country/region. The index score is derived by applying a formula that attaches values (weights) to each of the levels in each dimension. The EuroQol Group develops and maintains a collection of index values (weights) for all possible EQ-5D health states for specific countries/regions.

3.3.3. Immune Response Endpoints

1. Immune response (anti-drug antibodies [ADA] and T cell response) to mini-dystrophin transgene protein through Year 1 Week 52.
2. Immune response (ADA, T cell response and neutralizing antibodies [NAb]) to AAV9 through Year 1 Week 52.

ADA and NAb immune responses are provided as Positive or Negative with associated titers. ELISpot immune responses are provided for each of 3 peptide pools as Positive or Negative with associated response levels.

3.3.4. Viral Vector Shedding Endpoints

Whole blood, saliva, and urine samples for viral vector shedding kinetics will be collected in approximately the first 45 treated participants (approximately 30 treated with fordadistrogene movaparvovec and approximately 15 treated with placebo). For each randomized participant, sample collection for a particular matrix (sample type) will be stopped when at least 2 consecutive negative results are observed in that matrix.

Viral vector levels (vector genomes /ml), measuring intact and fragmented copies, will be determined in whole blood, saliva and urine using qPCR analysis. Additionally, intact viral vector levels (vector genomes/mL) in saliva and urine samples will be measured as intact copies following treatment with Micrococcal Nuclease (MNase). Viral vector shedding results below the lower limit of quantification (BLQ) for each matrix are considered negative or “undetectable. [Section 6.3.8](#) describes the approach for handling results that are undetectable.

For each of the 5 viral vector level profiles, one without MNase treatment for whole blood, one without MNase for saliva, one with MNase for saliva, one without MNase for urine, and one with MNase for urine, the following endpoints will be determined:

- Peak viral vector levels (vg/ml) post fordadistrogene movaparvovec administration.

Defined as the largest detectable result collected prior to the first set of 2 consecutive negative results.

- Time in weeks to peak viral vector shedding post fordadistrogene movaparvovec administration.

Defined as the time in weeks from the date of fordadistrogene movaparvovec administration to the peak viral vector result defined above.

- Time in weeks to undetectable viral vector (time to clearance of viral vector) from date of fordadistrogene movaparvovec administration.

The first set of 2 consecutive negative results is identified and then time to undetectable viral vector is defined as the time in weeks from the date of fordadistrogene movaparvovec administration to the first of the 2 consecutive negative results identified. If at the time of analysis, the last result is positive or negative results have not been confirmed, the time is recorded at the last date on which a sample for the particular matrix occurs and will be marked as censored for the analysis, meaning the time to undetectable viral vector clearance is at least that value.

- Time in weeks to the last undetectable viral vector from date of fordadistrogene movaparvovec administration

The first set of 2 consecutive negative results is identified and then time to last undetectable viral vector is defined as the time in weeks from the date of fordadistrogene movaparvovec administration to the last of the 2 consecutive negative results. If at the time of analysis, the last result is positive or negative results have not been confirmed, the time is recorded at the last date on which a sample for the particular matrix occurs and will be marked as censored for the analysis, meaning the time to undetectable viral vector clearance is at least that value.

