6.3.8. Viral Vector Shedding

Samples collected for viral vector shedding are only assayed for Cohort 1 (initially fordadistrogene movaparvovec) participants.

Note that there may be participants for which sample collection may continue after 2 consecutive undetectable samples because notification to stop may be provided after the participant has had another scheduled visit where a sample was to be collected or a site may mistakenly collect a sample after receiving notification to stop sample collection.

Endpoint:

- Peak viral vector levels (vg/ml) post fordadistrogene movaparvovec administration for each of the five profiles – one without MNase treatment for whole blood, one without MNase for saliva, one with MNase for saliva, one without MNase for urine, one with MNase for urine

Analysis:

- Analysis set: Viral Vector Shedding subset of Safety Analysis Set (through Week 52) ([Section 4](#)).
- Analysis methodology: Not applicable.
- Missing data: Missing/undetectable results will not be imputed.
- N, mean, SD, median, Q1, Q3, minimum, and maximum will be provided .

Endpoint:

- Time in weeks of peak viral vector shedding post fordadistrogene movaparvovec administration for each of the five profiles – one without MNase treatment for whole blood, one without MNase for saliva, one with MNase for saliva, one without MNase for urine, one with MNase for urine

Analysis:

- Analysis set: Viral Vector Shedding subset of Safety Analysis Set (through Week 52) ([Section 4](#)).
- Analysis methodology: Not applicable.
- Missing data: Missing/undetectable results will not be imputed.
- N, mean, SD, median, Q1, Q3, minimum, and maximum will be provided.

Endpoint:

- Time in weeks to undetectable viral vector (time to clearance of viral vector) from date of fordadistrogene movaparvovec administration for each of the five profiles – one without MNase treatment for whole blood, one without MNase for saliva, one with MNase for saliva, one without MNase for urine, one with MNase for urine.
- Time in weeks to the last undetectable viral vector from date of fordadistrogene movaparvovec administration for each of the five profiles – one for whole blood, two for saliva, two for urine.

Analysis:

- Analysis set: Viral Vector Shedding subset of Safety Analysis Set (through Week 52) ([Section 4](#)).

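### Time to vector clearance does not require an earlier detectable result, so a never-detected profile becomes a clearance event at about week 0 and a peak after two early negatives is not counted

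*SAP*

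**What the plan says.** All four shedding endpoints in SAP Section 3.3.4 are tied to one pair of samples.

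- **Time to undetectable:** "The first set of 2 consecutive negative results is identified and then time to undetectable viral vector is defined as the time in weeks" from dosing to the first of the pair.
- **Time to last undetectable:** "The first set of 2 consecutive negative results is identified and then time to last undetectable viral vector is defined as the time in weeks". The clock again starts at dosing, but it now runs "to the last of the 2 consecutive negative results".
- **Peak:** "Defined as the largest detectable result collected prior to the first set of 2 consecutive negative results". Time to peak is the time to that result.
- **Negative:** "Viral vector shedding results below the lower limit of quantification (BLQ) for each matrix are considered negative or" undetectable.
- **Censoring:** "If at the time of analysis, the last result is positive or negative results have not been confirmed, the time is recorded at the last" sample date for that matrix and is marked as censored.
- **Sampling:** "sample collection for a particular matrix (sample type) will be stopped when at least 2 consecutive negative results are observed in that matrix".

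The Viral Vector Shedding population in Section 4 needs two post-baseline measurements within 7 days of dosing, but not a detectable one. Section 3.3.4 refers to Section 6.3.8 for undetectable results. Section 6.3.8 says only that they are not imputed, and it reports Kaplan-Meier 25th, 50th and 75th percentiles. It adds: "Note that there may be participants for which sample collection may continue after 2 consecutive undetectable samples". Section 5.2.2 refers back to Section 3.3.4 for censoring.

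**The concern.** Time to clearance describes how long vector remains detectable once it has appeared. As written, the rule puts three groups into one event: boys who shed and cleared, boys never detectable in that profile, and boys whose first two samples were negative but who were positive later. The last two receive an event time at or near zero.

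No other section separates them. The analysis population does not, Section 6.3.8 does not, and the censoring sentence does so only in part. The peak definition adds a second loss: when the negative pair comes first, no result precedes it, so a later detectable value counts towards neither peak nor time to peak. At stake is whether the shedding percentiles and peak summaries mean what their labels say. Any error in the clearance percentiles makes shedding look shorter.

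**Working it through.** The SAP gives no figure for this endpoint, so there is nothing to reproduce. The check applies the rule literally.

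**Inputs.** Target days from Appendix 2.1: saliva and urine 1, 2, 4, 7, 10, 14, 21, 34, 60, 90, 120, 240, 360; whole blood 2, 4, 21, 60, 90, 120, 240, 360. About 30 actively treated boys are sampled (Section 3.3.4). The SAP does not fix the day convention for this endpoint, so both day/7 and (day − 1)/7 are shown.

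**Step 1: hypothetical profiles.** Results not listed as positive are negative.

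| Profile | Clearance as written, weeks: day/7 [(day − 1)/7] | Peak as written | Clearance if an earlier positive is required (day/7) |
|---|---|---|---|
| Saliva/urine, never detected | 1/7 = 0.14 [0.00] | none | no event |
| Saliva/urine, negative Days 1–2, positive Days 4–21 | 0.14 [0.00] | none | 34/7 = 4.86 |
| Saliva/urine, negative Day 1 only, positive Days 2–21 | 4.86 [4.71] | counted | 4.86 |
| Saliva/urine, positive Day 1, negative Days 2 and 4, positive Days 7–14 | 2/7 = 0.29 [0.14] | Day 1 value only | 0.29 |
| Whole blood, never detected | 2/7 = 0.29 [0.14] | none | no event |
| Whole blood, negative Days 2 and 4, positive Days 21–60 | 0.29 [0.14] | none | 90/7 = 12.86 |
| Whole blood, positive Days 2–60 | 12.86 [12.71] | counted | 12.86 |

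Time to last undetectable moves in the same way. In the second row it is 2/7 = 0.29 weeks as written, against 60/7 = 8.57.

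The usual course, positive first and negative later, is unaffected. One early negative does no harm; two are needed. The rebound in the fourth row is not repaired by requiring an earlier positive, so it needs its own rule.

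**Step 2: effect on the percentiles.** Suppose a share p of profiles is placed at time 0, the shedders' clearance times have distribution F, and nothing is censored. The reported distribution is p + (1 − p)F(t). Setting this to 0.5 gives F(t) = (0.5 − p)/(1 − p):

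- p = 0.1: 0.4/0.9 = 0.444
- p = 0.2: 0.3/0.8 = 0.375
- p = 0.3: 0.2/0.7 = 0.286

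The reported 25th percentile reaches about 0 at p = 0.25, and the median at p = 0.5.

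**Step 3: the same on the sampling grid.** Assume n = 30, shedders' clearance spread evenly over Days 14, 21, 34, 60, 90 and 120, and the early-pair profiles placed at Day 1 (day/7). Weeks:

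| p | 25th | Median | 75th |
|---|---|---|---|
| 0 | 3.00 | 4.86 | 12.86 |
| 0.1 | 2.00 | 4.86 | 12.86 |
| 0.2 | 2.00 | 4.86 | 12.86 |
| 0.3 | 0.14 | 3.00 | 8.57 |
| 0.4 | 0.14 | 2.00 | 8.57 |
| 0.5 | 0.14 | 0.14 | 4.86 |

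Shedders alone give 3.00, 4.86 and 12.86 at every p. On this coarse grid the median does not move up to p = 0.2, although the 25th percentile already does. Both p and the spread of clearance times are assumptions.

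**The case against.** Much of the case on the other side stands.

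- **Positives after the first pair.** A reader might infer that the SAP expects them. It does not: Section 6.3.8 says only that collection may continue, through late notification or site error. They are possible for that reason, and because stopping is per matrix while the endpoints are per profile, with and without MNase.
- **Censoring.** A reader might also infer that a later positive can never change the clearance date. The censoring sentence can be read to cover a boy whose last result is positive. However, it competes with the first-pair rule, no precedence is given, and it does not reach a boy who turns negative again.
- **Sampling.** The stop rule means that many late peaks would never be collected, and no SAP wording can recover those.
- **Mechanism and use.** Nothing in the SAP shows that vector reaches saliva or urine late, that the MNase profiles are most exposed, or that the results are meant for assessing exposure of other people. The point does not rest on any of these.
- **Estimand choice.** A boy always below the limit is, in a sense, undetectable from his first sample. That is defensible if stated, but the SAP also calls this endpoint time to clearance, and nothing was there to clear.
- **Visibility.** N for peak, the range and the Kaplan-Meier curve would show signs of the problem. They would not say which early events were never-detected profiles.

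**Conclusion.** The point holds as a minor one. The stated rule gives a clearance event at the first sample for a never-detected profile, which needs no assumption about vector kinetics. It gives the same near-zero time and no peak for a profile whose first two samples are negative and which is later positive on file.

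The direction is towards shorter reported shedding. The size cannot be stated, because the SAP does not give the share of such profiles. In the illustration the 25th percentile falls from 3.00 to 2.00 weeks at an assumed 10 to 20%, and the median changes only from 30%. The exact week-0 value also assumes that the Day 1 saliva or urine sample is post-dose and that time is counted as day minus 1. If Day 2 were the first sample, the event would fall at 0.14 or 0.29 weeks.

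A reader might infer a threat to the trial's conclusions. The documents do not support that: the objective is tertiary/exploratory, the summaries are descriptive, and only Cohort 1 samples are assayed.

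**What to change.** In Sections 3.3.4 and 6.3.8:

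1. Define time to undetectable and time to last undetectable from the first two consecutive negatives that follow at least one detectable post-dose result.
2. Report profiles with no detectable result as never detected, n (%), separately from the Kaplan-Meier estimate for that profile.
3. Define peak as the largest detectable post-dose result in the reporting period, with time to peak following from it.
4. State whether the first-pair rule or the censoring rule takes precedence when a positive follows a negative pair, and list such cases.

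A tempting stricter version would require that no later available sample be positive. That would make clearance depend on which boys happened to be sampled beyond the stop notice, so a stated precedence rule with a listing is preferable.

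The cost is SAP wording and a small programming change, with no new samples. The Kaplan-Meier denominator shrinks in some profiles and describes shedders only, which the separate count makes plain. Late shedding that was never sampled because collection had stopped remains unknown.
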